## **B.6. Aim 3: Conduct Joint Pilot Projects**

We will complete two joint pilot projects that will demonstrate the Center’s ability to collaborate effectively, engage partners from multiple sectors, and develop and conduct preliminary evaluations of interventions at multiple levels of impact (e.g., individual, social, environmental, community).

### **B.6.1. Pilot Study # 1: Promoting physical activity (PA) among breast cancer survivors in Colombia**

**Rationale:** Breast cancer is the most common cancer in women worldwide. In Colombia, nearly 5,000 new cases are diagnosed annually. PA is associated with decreased cancer risk. A growing body of evidence supports the idea that increasing PA provides important benefits to psychological and physical wellbeing in breast cancer patients. We will design a theory-based intervention to integrate PA promotion into clinical care for breast cancer survivors, with the ultimate goal of secondary prevention and enhanced survival.

**Methods:** We will conduct a small, randomized controlled study of a PA intervention among 60 breast cancer patients (18-65 years). Eligible women will be randomized to the PA intervention or a control group that will receive an education program not related to PA. The intervention will include supervised exercise through dancing and a culturally relevant and piloted smartphone app aimed at promoting PA and decreasing sedentary behavior. The primary outcomes for this pilot will be weekly minutes of PA, quality of life, and mental health – specifically, anxiety and depression. This project will involve partnerships between researchers at Stanford School of Medicine, the Institute of Sports and Recreation in Bogotá, the Universidad del Rosario, the Foundation Simmon, the National Cancer Institute of Colombia, and UniAndes.

**Analysis:** We will use a mixed methods approach to assess acceptability, feasibility, and preliminary effectiveness of the intervention. **Acceptability/feasibility:** Qualitative methods will include focus group discussions with participants at the conclusion of the study to explore acceptability and feasibility. Non-participants will be included in focus groups to examine factors influencing participation. Quantitative methods will include ratings of intervention components to capture acceptability, practicality, and motivational capabilities on a Likert-type 7-point scale (with a goal of obtaining acceptability mean ratings  $\geq 6$  out of 7). **Preliminary effectiveness:** To assess preliminary effectiveness, we will use repeated measures ANOVA, Kruskal–Wallis and McNemar tests to establish the change in outcomes before and after treatment. Outcomes will include physical activity/sedentary behavior, health-related quality of life, and anxiety and depression. (All measures have been tested in and shown to be appropriate for Latino populations.)

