**Analysis:** We will use mixed methods to assess the longitudinal impact of the Ciclovía/Recreovía on physical activity levels among adults and children. For qualitative methods, we will use the citizen scientist *Nuestra Voz* (Our Voice) model that employs a tablet-based application to empower residents to document features of their neighborhoods that promote and hinder physical activity. Drs. [name], [name], and [name] have successfully used this approach in diverse communities including with Latinos in the US and in Latin America. For quantitative methods, we will assess the median differences in moderate to vigorous PA (pre-post) and interquartile range (IQR) of the self-reported and objectively measured (via accelerometers) PA outcomes, which will be compared using the Wilcoxon Signed Rank Test.

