## **B.8. Sustainability and Future Directions**

The ultimate goal of the activities planned during this 2-year period are to create, enhance, and support the infrastructure and capacities that are needed to maintain a sustained effort focused on NCD prevention in Colombia and the Latin American region. This project is built on an existing partnership that has already successfully maintained collaborations and will expand to engage additional partners from diverse sectors, thus promoting sustainability. The partnership development activities will promote sustained engagement in research activities. Research enhancement activities, including scholar exchanges and various training programs, are designed not only to sustain research activities, but also to expand and grow these activities over time and throughout the Latin American region. Finally, the pilot projects are aimed at producing the necessary preliminary experience and evidence to support future larger scale projects. As described in **Table 1** of the **Planning Unit** description, short- and mid-term goals include submitting proposals for larger-scale studies that build on findings from the pilot studies.

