4.2 Finalize short-, mid-, and long-term goals and expected outcomes.	
Short-term:
 
 
Multi-sectoral partners engaged to finalize goals and outcomes
 
Goals and outcomes disseminated through policy briefs for key stakeholders
 
 
Mid- & long-term:
 
 
Goals and outcomes continuously communicated back to partners
 
	
 
CBPR approach will ensure that multiple stakeholders from various sectors are invested in the goals and outcomes to promote sustainability
 
	
 
Goals and outcomes will be focused on policy changes to sustain NCD prevention policies and outcomes
 

**B.6.1. Steps to enhance longevity of activities.** By employing a socio-ecological model and utilizing a CBPR orientation to research, all S-C priorities are designed to promote long-term sustainability of research plans, enhancement activities, and shared core facilities. The strategies for promoting long-term sustainability are provided in **Tables 1A-D**. To summarize, key strategies to promote long-term sustainability of S-C plans

include: 1) The training program we propose will help ensure longevity by training a cadre of scientists in behavioral intervention research and leaving in place courses and a Masters Program in Epidemiology; 2) We will engage the major stakeholders in this project as voting members of the Steering Committee since they represent sectors that will facilitate longevity of the program; and 3) We intend to use the pilot studies to generate preliminary results to seek major NIH grants in addition to other sources of funding to enable us to continue and enhance continuing research activities.

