Evidence-based strategies to promote physical activity encompass approaches that target individuals, their families, the neighborhoods in which they live, work, and play, and the policies that shape their opportunities for leading active lives. Additionally, physical activity interventions are easily culturally targeted and tailored, especially when community-based participatory research approaches are employed, making them an ideal approach for reducing NCD risk in regions such as Latin America with rich and heterogeneous cultural backgrounds. To support such potentially effective approaches, significant investment in the research capacity in the region is needed. Currently, in Colombia and the Latin American region, research has focused largely on observational methods for physical activity surveillance and examination of multi-level determinants of physical activity levels (e.g., individual, family, and neighborhood). With this critically important information on activity levels and determinants, the region now has an opportunity to build upon this foundation to create a body of research focused on behavior change through multiple levels of influence. The plans for research studies, research enhancement, and shared core facilities will be informed by the mixed methods needs assessment as described in the Coordinating Unit.

The Specific Aims of the Planning Unit are the following:

**1. Complete two pilot studies of physical activity interventions that focus on distinct levels of influence in diverse populations.** One pilot study will use a randomized controlled trial design to examine the preliminary effectiveness of a physical activity intervention for breast cancer patients. A second pilot study will use a longitudinal cohort design of Ciclovías and Recreovías in Colombia.

**2. Take advantage of Stanford's expertise in core research areas to train world leaders in behavioral science research at Universidad de los Andes to support regional expertise in physical activity intervention research.** A multi-pronged educational approach is planned for increasing research capacity among research partners, students, and community members. Activities will include developing a masters of science degree, a professional certificate program, and mini-courses for key stakeholders.

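### Pilot Study #1 names no between-arm estimate or baseline adjustment; where repeated measures ANOVA is used, ANCOVA would usually be more precise on the same 60 women

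*Combined protocol and SAP*

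**What the plan says.** The Overall Plan, B.6.1, describes a randomised study of 60 breast cancer patients: "Eligible women will be randomized to the PA intervention or a control group that will receive an education program not related to PA". It lists the endpoints: "The primary outcomes for this pilot will be weekly minutes of PA, quality of life, and mental health – specifically, anxiety and depression". The Planning Unit's Specific Aims give the purpose of randomising: "One pilot study will use a randomized controlled trial design to examine the preliminary effectiveness of a physical activity intervention for breast cancer patients".

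The effectiveness analysis in B.6.1 is a single sentence: "To assess preliminary effectiveness, we will use repeated measures ANOVA, Kruskal–Wallis and McNemar tests to establish the change in outcomes before and after treatment". It does not say:

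- which outcome goes to which test;
- how many visits there are;
- which ANOVA term is tested (time, group, or group-by-time);
- whether baseline is a covariate;
- whether a between-arm difference with an interval will be reported.

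No other section supplies these for Pilot Study #1.

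**The concern.** A randomised trial answers a question about effectiveness by comparing the arms. The planned sentence speaks only of change from before to after, so two readings are open.

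- **Time effect only.** The control arm is not used as a comparator and there is no between-arm estimate.
- **Group-by-time on two visits.** This is the same as a t-test on change scores. It is valid, but it fixes the slope of follow-up on baseline at 1. ANCOVA estimates that slope and is usually more precise.

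The results are meant to be used. Overall Plan B.8 says "the pilot projects are aimed at producing the necessary preliminary experience and evidence to support future larger scale projects", and Coordinating Unit B.6.1 says "We intend to use the pilot studies to generate preliminary results to seek major NIH grants". The likely cost of the present wording is a wider between-arm interval than the same data allow, or no such estimate. The documents do not say that the interval will be used to plan later trials; that is an inference.

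**Working it through.** The documents state no power, effect size, SD, correlation or dropout for this pilot, so there is no planned figure to reproduce. The check compares the precision of two analyses of the same data.

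**Inputs.** From the documents: N = 60, two randomised arms. Assumed: 30 per arm, all followed up, one baseline and one follow-up visit, a normally distributed baseline, correlation ρ = 0.3, 0.5 or 0.7, and k = baseline SD / follow-up SD from 0.7 to 1.3. The follow-up SD is set to 1.

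**Formulas (variance per woman).**

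- Change score: 1 + k² − 2ρk.
- ANCOVA: (1 − ρ²) × (1 + 1/(N − 4)). The second factor is the expected cost of estimating the slope. At N = 60 it is 1 + 1/56 = 1.0179.

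The ratio of the two, minus 1, is the gain from ANCOVA expressed as extra patients.

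**Worked example, k = 1 and ρ = 0.3.** Change score: 1 + 1 − 0.6 = 1.40. ANCOVA: 0.91 × 1.0179 = 0.926. Ratio: 1.40 / 0.926 = 1.511, a gain of 51%.

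| k | ρ = 0.3 | ρ = 0.5 | ρ = 0.7 |
|---|---|---|---|
| 0.7 | 1.155 | 1.035 | 0.982 |
| 0.8 | 1.252 | 1.100 | 1.002 |
| 0.9 | 1.371 | 1.192 | 1.060 |
| 1.0 | 1.511 | 1.310 | 1.156 |
| 1.3 | 2.062 | 1.821 | 1.676 |

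At k = 1, 60 women analysed by ANCOVA match 60 × 1.511 ≈ 91, 60 × 1.310 ≈ 79 and 60 × 1.156 ≈ 69 women analysed by change scores. A simulation of 40,000 trials per setting gave 1.50 (k = 1, ρ = 0.3), 1.15 (k = 1, ρ = 0.7), 0.98 (k = 0.7, ρ = 0.7) and 2.06 (k = 1.3, ρ = 0.3).

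**Where ANCOVA gains nothing.** Apart from the small-sample factor, the two variances differ by (1 + k² − 2ρk) − (1 − ρ²) = (k − ρ)². Break-even is at (k − ρ)² = (1 − ρ²)/56, so k = ρ ± 0.127, 0.116 and 0.095. There is no gain when k lies in:

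- 0.17 to 0.43 (ρ = 0.3);
- 0.38 to 0.62 (ρ = 0.5);
- 0.60 to 0.80 (ρ = 0.7).

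The worst case is k = ρ, where the ANCOVA variance is 1.8% larger.

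**Interval width.** The 95% half-width is t × √(variance × 2/30), with 58 df for change scores and 57 for ANCOVA, in follow-up SDs. Each cell shows change score, then ANCOVA:

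| k | ρ = 0.3 | ρ = 0.5 | ρ = 0.7 |
|---|---|---|---|
| 0.8 | 0.56 to 0.50 | 0.47 to 0.45 | 0.37 to 0.37 |
| 1.0 | 0.61 to 0.50 | 0.52 to 0.45 | 0.40 to 0.37 |

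**Sensitivity.** With 48 completers (20% loss, assumed) the factor is 1 + 1/44 = 1.0227. The k = 1 gains are then 50%, 30% and 15%, and the worst penalty is 2.3%. If the ratio 0.7 to 1.3 is instead read as follow-up SD over baseline SD, the range is about −1% to +136%.

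**The case against.** The efficiency figures rest on several conditions that the documents do not state: an outcome assigned to ANOVA, exactly two visits, a group-by-time test, and an assumed correlation and SD ratio. The resulting range runs from a slight loss to a doubling. If women respond differently to the intervention, the follow-up SD may exceed the baseline SD (also an assumption). At k = 0.7 to 0.8 the gain is then only −2% to 25%. The change-score test is valid, so on that reading this is a choice between two sound methods. Kruskal-Wallis compares independent groups, which suggests that some comparison of arms is intended.

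The stakes are also modest. Planning Unit B.1.5 puts acceptability and feasibility among the short-term aims, and its goals table expects no change in health outcomes in that period. Table 1C of the Coordinating Unit places documented behaviour change in the mid and long term. Weekly activity minutes, the first-listed primary outcome, may not go to ANOVA at all. Pilot Study #2 summarises self-reported activity, citing the same questionnaire, by medians, "which will be compared using the Wilcoxon Signed Rank Test" (Overall Plan, B.6.2).

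All of this limits the size and rank of the point, and the figures should be read as illustrations. It does not supply the missing model term or between-arm estimate. Nor does it give a reason to prefer the unadjusted analysis, since the expected cost of ANCOVA is at most about 2% in variance.

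**Conclusion.** The point holds, as an improvement to consider. For a two-arm randomised comparison, the plan names no tested ANOVA term, baseline covariate or between-arm estimate.

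If the ANOVA is group-by-time on two visits, its result is valid, but ANCOVA is worth 16% to 51% more patients at equal SDs. Over baseline-to-follow-up SD ratios of 0.7 to 1.3 the range is −2% to +106%. Correlation (0.3 to 0.7), SD ratio, two visits and complete follow-up are all assumed.

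If only the time effect is tested, these figures do not apply and the gap is larger, because there is no between-arm estimate. With more than two visits the figures would differ. They do not extend to outcomes analysed by the Kruskal-Wallis or McNemar tests.

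**What to change.** For each outcome analysed as continuous, replace repeated measures ANOVA with ANCOVA of the follow-up value on arm and baseline value, or an equivalent constrained longitudinal model. Report the adjusted between-arm difference with its 95% CI as the preliminary effectiveness estimate. State the number of visits, which outcomes this covers, and which go to the Kruskal-Wallis or McNemar tests.

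The cost is SAP wording. A before-and-after analysis already needs the baseline values, so no new data, visits or patients are required. The statistical price is an expected variance penalty of at most about 2% at N = 60, incurred only when the SD ratio is close to the correlation.

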## A. Specific Aims (Planning Unit)

The goal of the Planning Unit for the Stanford-Colombia Collaboratory on Chronic Disease (S-C) is to provide a structured roadmap for a set of coordinated activities aimed at increasing research capacity in the Latin American region for reducing the prevalence of non-communicable diseases (NCDs) through promotion of physical activity. Colombia is uniquely positioned to serve as a regional leader given the country's academic resources (e.g., Universidad de los Andes), emerging governmental support of NCD prevention, and numerous partnerships throughout the region. Stanford researchers, who have an existing strong collaboration with researchers at Universidad de los Andes (UniAndes), will act as a catalyst by providing strategic scientific and academic support to increase research capacity in the areas of behavioral science, technology, measurement and data analysis, and community engagement and translation methods.

The high burden of (NCDs) in low- to middle-income countries (LMIC) in Latin America, such as Colombia, calls for a highly coordinated, effective, and innovative research strategy to develop, test, and disseminate prevention and management strategies with high potential to improve population health. Close to 7 in 10 deaths in Latin America are due to NCDs, including cancer, cardiovascular disease (CVD), and type 2 diabetes. Fortunately, NCDs are largely preventable through low-cost, non-invasive, and culturally centered strategies such as promotion of guideline-concordant physical activity. Moderate- to vigorous-intensity physical activity (PA) of 150 minutes per week among adults and 60 minutes per day among children is associated with substantially lower lifetime risk of NCD. There is enormous opportunity to prevent NCDs in the Latin American region through promotion of physical activity given increasingly low levels of PA and high levels of sedentary behavior. In Colombia, 47% of adults and 74% of adolescents do not meet physical activity recommendations, comparable to levels in the US and higher than other Latin American countries such as Mexico, Ecuador, and Uruguay. If left unaddressed, physical activity levels in Latin America will continue to decline, with corresponding increases in NCD prevalence.

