Health and policy outcomes	
Health outcomes:
 
 
Changes in health outcomes are not expected in the short-term
 
 
Policy outcomes:
 
 
Policy changes are not expected in the short term
 
	
Health outcomes:
 
 
Preliminary evidence of increases in physical activity among certain subgroups targeted in research studies is documented in Colombia
 
 
Policy outcomes:
 
 
Initial changes in policies related to NCD prevention research are documented in Colombia and the Latin American region
 
Changes in Colombian policies to support active living are documented
 
	
Health outcomes:
 
 
Increasing evidence of increases in physical activity is documented in Colombia and the Latin American region
 
 
Policy outcomes:
 
 
Sustained political support for NCD prevention research is documented in Colombia and the Latin American region
 
Changes in policies to support active living are documented in Colombia and the Latin American region
 

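### Pilot 1 randomises women to two arms, but its effectiveness analysis targets before-to-after change and names no between-arm contrast; McNemar cannot supply one.

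*Combined protocol and SAP*

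**What the plan says.** The Methods paragraph of B.6.1 (Overall Plan) sets up a two-arm randomised comparison in 60 patients: "Eligible women will be randomized to the PA intervention or a control group that will receive an education program not related to PA". It then fixes the endpoints: "The primary outcomes for this pilot will be weekly minutes of PA, quality of life, and mental health", the last meaning anxiety and depression. The Planning Unit's Specific Aims say what the randomisation is for: "One pilot study will use a randomized controlled trial design to examine the preliminary effectiveness of a physical activity intervention for breast cancer patients".

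The Analysis paragraph of B.6.1 contains one sentence on how preliminary effectiveness will be analysed: "we will use repeated measures ANOVA, Kruskal–Wallis and McNemar tests to establish the change in outcomes before and after treatment". The sentence after it only lists the outcome domains and their instruments. For pilot 1 the documents give no between-arm contrast, effect estimate or confidence interval. They do not assign tests to outcomes, define a yes/no outcome or state when the post-treatment assessment takes place.

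**The concern.** The control arm is there to separate the effect of the programme from whatever would have happened anyway. Recovery over time, regression to the mean and repeated questionnaires can all move scores in both arms. A before-after test in the intervention arm, or a time effect pooled over arms, includes that shared movement; a between-arm comparison removes it.

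The stated target is change over time, and one of the three named tests cannot use the control arm. An analyst could therefore follow the sentence, report time effects and McNemar results as preliminary effectiveness, and still comply with the plan. The affected outcomes are the ones called primary, and the Coordinating Unit's plan (B.6.1, on longevity of activities) gives the results a further use: "We intend to use the pilot studies to generate preliminary results to seek major NIH grants in addition to other sources of funding". A before-after gain taken for a treatment effect would then carry over into the case for a larger study.

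**Working it through.** **What each named test can do with two parallel arms measured before and after**

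- *Repeated measures ANOVA.* It gives a time main effect (change averaged over arms) and, if arm is in the model, a group-by-time term (difference in change between arms). Only the second uses the randomisation. The sentence names neither, and its wording is closer to the first.
- *Kruskal–Wallis.* This is a test for independent groups. Applied to change scores by arm it is a between-arm test. The sentence does not say what is ranked or which groups are compared.
- *McNemar.* It compares paired yes/no responses. No matched-pair randomisation is described, so the pairs are the same women before and after. It describes within-arm change and cannot compare arms. The pilot 1 outcomes are minutes and scale scores, and no cut-off is adopted for them.

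The plan gives no calculation behind its sample size of 60, so there is no figure to reproduce.

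**Illustration: the cost of reading before-after change as effectiveness**

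From the documents: 60 women, two arms. Assumed: 1:1 allocation (n = 30 per arm), no dropout, two-sided 5% tests, normal outcomes with SD 1 at each time, pre-post correlation ρ = 0.3, 0.5 or 0.7, no true effect, and the same drift δ (in SD) in both arms.

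The SD of change is √(2(1−ρ)) = 1.183, 1.000, 0.775. The intervention-arm paired t-test has 29 df and noncentrality δ√30 / √(2(1−ρ)). At δ = 0.2 and ρ = 0.5 this is 0.2 × 5.477 / 1.000 = 1.095, which gives a rejection probability of 0.185. All settings:

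| Drift δ | ρ = 0.3 | ρ = 0.5 | ρ = 0.7 |
|---|---|---|---|
| 0.1 | 0.073 | 0.083 | 0.105 |
| 0.2 | 0.146 | 0.185 | 0.277 |
| 0.3 | 0.269 | 0.355 | 0.536 |
| 0.5 | 0.609 | 0.754 | 0.927 |

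Under the same conditions, simulation (10,000 runs per setting) puts the between-arm tests at their nominal level: group-by-time 4.5–5.3%, ANCOVA 4.4–5.3%, Kruskal–Wallis on change 4.5–5.3%.

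For McNemar, suppose the yes/no outcome were meeting PA recommendations, with 30–53% meeting them at baseline. The upper value is the complement of a national figure, "In Colombia, 47% of adults and 74% of adolescents do not meet physical activity recommendations" (100 − 47 = 53); applying it to these women is an assumption. With no true effect and the same rise in both arms (40,000 runs per setting), exact McNemar in the intervention arm is significant in 8–10% of trials for a 10-point rise and 29–42% for a 20-point rise. Comparing post-treatment proportions between arms stays at 4.4–5.3%.

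**Precision of the two between-arm options (normal outcomes)**

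The 95% CI half-width is t × SD × √(2/30), with √(2/30) = 0.258.

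- Group-by-time (SD √(2(1−ρ)), 58 df, t = 2.002): 0.612, 0.517, 0.400 SD for ρ = 0.3, 0.5, 0.7.
- ANCOVA on baseline (SD √(1−ρ²), 57 df, t = 2.002): 0.493, 0.448, 0.369 SD.

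**Skewed PA minutes**

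This advantage does not carry over to strongly skewed minutes. With lognormal values at log-SD 1.2 and 30 per arm, raw-scale ANCOVA intervals cover about 93–94% under a proportional effect. Under an additive shift of 0.3 SD, ANCOVA has 38–50% power against 64–91% for Kruskal–Wallis on change.

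**The case against.** The best defence is that a comparison by arm was intended and written tersely. The design is described as a randomised trial to examine preliminary effectiveness. Group-by-time is a standard term of a two-group repeated measures ANOVA. Kruskal–Wallis cannot test paired change at all, so naming it suggests a comparison of groups. Where the documents have a pre-post question, in the Ciclovía/Recreovía cohort (B.6.2), they name a paired test: the outcomes are those "which will be compared using the Wilcoxon Signed Rank Test". This stands. A reader might infer that none of the named tests can compare arms, or that the team means to ignore its control group; the documents support neither. For these two tests the fault is a missing statement.

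McNemar also has a legitimate use: it can describe within-arm change in a yes/no status. The Planning Unit's Specific Aims mention 150 minutes of activity a week for adults, which would be a natural threshold, but pilot 1 does not adopt it. So it would go too far to call McNemar useless here. What stands is that it cannot be evidence of effectiveness and that no outcome is defined for it.

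Two further points are fair. The high error rates arise only if the control arm is left out of the inference, and they depend on drift for which the documents give no basis. And this is a small pilot, concerned also with acceptability and feasibility, with no stated alpha, power or decision rule. Both limit the consequence. Neither tells the analyst which contrast to report.

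**Conclusion.** The point holds as an under-specified effectiveness analysis whose stated target and one of whose named tests do not use the randomisation. It should be fixed. That conclusion rests on the text alone.

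The size is conditional. If before-after change is read as effectiveness, a nominal 5% test becomes one that is significant in 7–28% of null trials at 0.1–0.2 SD of shared drift and 27–93% at 0.3–0.5 SD. This assumes 30 per arm, normal outcomes and pre-post correlation 0.3–0.7. If the team already intends a between-arm test, the error rate stays near 5% and the remedy is to say so. A reader might take the 93% as the plan's false-positive rate; it is not, because the plan does not commit to the before-after reading.

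**What to change.** Replace the sentence with a statement that, for each primary outcome, the effect is the difference between randomised arms, reported with a 95% CI.

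- *Minimum:* keep repeated measures ANOVA and name the group-by-time term as the effect. This removes the error.
- *Preferred:* ANCOVA of the post-treatment value with baseline as covariate. For roughly normal outcomes it narrows the half-width from 0.40–0.61 SD to 0.37–0.49 SD under the assumptions above.
- *Weekly PA minutes:* in case they are skewed, fix in advance either a rank-based comparison of change between arms or ANCOVA on a transformed scale. Do not assume that raw-scale ANCOVA needs no alternative.
- *Within-arm changes:* report them as descriptive only, and do not use McNemar as evidence of effectiveness. If a yes/no PA outcome is wanted, define it in advance and compare its proportion between arms with a 95% CI.
- *Timing:* state when the post-treatment assessment takes place.

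The cost is a change of text. The minimum version is a wording change apart from McNemar's role; the preferred version changes the named method. Neither needs more patients, visits or measures, because both use the before and after values and the allocation already planned.

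### Pilot 1 assigns Kruskal–Wallis, an independent-samples test, to before-to-after change: used literally it ignores pairing, is conservative, and loses power by an amount set by an unstated correlation

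*Combined protocol and SAP*

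**What the plan says.** Pilot 1 (Overall Plan, Section B.6.1, Methods) is a two-arm randomized study of 60 women: "Eligible women will be randomized to the PA intervention or a control group that will receive an education program not related to PA". Its outcomes are listed as follows: "The primary outcomes for this pilot will be weekly minutes of PA, quality of life, and mental health – specifically, anxiety and depression".

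The quantitative effectiveness analysis is one sentence in the Analysis paragraph of the same section: "we will use repeated measures ANOVA, Kruskal–Wallis and McNemar tests to establish the change in outcomes before and after treatment". All three tests share one stated purpose, which is change over time. No test is tied to an outcome, to a grouping factor or to a comparison of arms, and no change score is defined.

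Pilot 2 (Section B.6.2, Analysis) also has pre-post physical activity data. There the outcomes are to be "compared using the Wilcoxon Signed Rank Test", which is a paired rank test. Pilot 1 names no paired rank test.

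**The concern.** Repeated measures ANOVA and McNemar are built for repeated measurements on the same person. Kruskal–Wallis is not: it compares independent groups. If the groups are the before and after time points, the same women appear in both and the test's assumption fails.

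Kruskal–Wallis is also the only rank test that Pilot 1 offers. Activity minutes and bounded questionnaire scores are plausible candidates for a rank test, although the plan does not say which outcomes would go to it. The pilots are meant to support larger proposals (Overall Plan, Section B.8; Planning Unit, Section B.1.4). A test that hides real change would weaken the evidence carried into those proposals.

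**Working it through.** **Inputs.** From Section B.6.1: the three tests and their stated purpose, two randomized arms, and 60 women in total. The section gives no allocation ratio, significance level, power, effect size, standard deviation, dropout rate or before-after correlation, so there is no stated figure to reproduce. Assumptions: 30 women per arm, two time points, no dropout, normal scores with SD 1, a two-sided 5% level, and correlation r varied over a range.

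**1. Why pairing matters.** With n women, the mean change has variance 2σ²(1 − r)/n. A test that treats the two sets of scores as independent works with 2σ²/n. Under no change, its standardized statistic therefore has SD √(1 − r) instead of 1.

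**2. True size at nominal 5%** (normal approximation): 2Φ(−1.96/√(1 − r)).
- r = 0.3: 2Φ(−1.96/0.837) = 2Φ(−2.34) = 1.9%
- r = 0.5: 2Φ(−1.96/0.707) = 2Φ(−2.77) = 0.6%
- r = 0.7: 2Φ(−1.96/0.548) = 2Φ(−3.58) = 0.03%

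**3. Power where a paired test has 80%:** Φ(2.80 − 1.96/√(1 − r)).
- r = 0.3: Φ(0.46) = 68%
- r = 0.5: Φ(0.03) = 51%
- r = 0.7: Φ(−0.78) = 22%

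**4. Simulation.** This used 20,000 replicates of bivariate normal scores, with Kruskal–Wallis applied to before versus after. Power is taken at the shift where the paired t test has 80%. The relative loss is (signed-rank − Kruskal–Wallis)/signed-rank.

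| Pairs | r | Size, Kruskal–Wallis | Power, Kruskal–Wallis | Power, signed-rank | Relative loss |
|---|---|---|---|---|---|
| 30 | 0.3 | 0.0191 | 0.667 | 0.780 | 0.113/0.780 = 14% |
| 30 | 0.5 | 0.0065 | 0.496 | 0.776 | 0.280/0.776 = 36% |
| 30 | 0.6 | 0.0043 | 0.389 | 0.784 | 0.395/0.784 = 50% |
| 30 | 0.7 | 0.0013 | 0.236 | 0.783 | 0.547/0.783 = 70% |
| 60 | 0.3 | 0.0208 | 0.656 | 0.781 | 0.125/0.781 = 16% |
| 60 | 0.5 | 0.0072 | 0.497 | 0.781 | 0.284/0.781 = 36% |
| 60 | 0.7 | 0.0008 | 0.221 | 0.784 | 0.563/0.784 = 72% |

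The signed-rank test held its size (0.046 to 0.053 with 30 pairs). Doubling the number of pairs does not repair the size of Kruskal–Wallis. Lognormal scores gave the same pattern, with size 0.007 at r = 0.5 and 0.001 at r = 0.7.

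**5. Dependence on the effect.** For a fixed shift of 0.5 SD, power (Kruskal–Wallis against signed-rank) is:
- 30 pairs: 0.45 against 0.74 at r = 0.5, and 0.44 against 0.92 at r = 0.7
- 60 pairs: 0.83 against 0.96 at r = 0.5, and 0.89 against 0.997 at r = 0.7

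**6. The valid use.** Kruskal–Wallis on change scores, 30 against 30 women, had size 0.049 at both r = 0.5 and r = 0.7. With two groups it is equivalent to the rank-sum test.

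**The case against.** The strongest reply is that the sentence does not fix the contrast. The trial has two independent arms, and Planning Unit Specific Aim 1 says that the randomized design is there to examine preliminary effectiveness. The authors could have meant Kruskal–Wallis on change scores between arms, which is valid. Having two arms does not rule this out, because the test works with two groups. The signed-rank test in Pilot 2 also cuts both ways: it shows that the authors know the paired test, so a different choice in Pilot 1 might signal a different contrast.

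Part of this stands. A reader might infer that the plan definitely treats each woman's two scores as independent samples. The documents do not establish that; it is the literal reading but not the only possible one. The benign reading, however, needs both an arm contrast and a derived change score, and neither is stated there or elsewhere in the documents. It would also leave Pilot 1 with no rank test for within-arm change. The sentence needs amending on either reading.

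A reader might also infer that most of the paired power is lost. That holds only from r of about 0.6 upward, near the 80% power point. It fails at r = 0.5 or below there, and for a 0.5 SD shift with all 60 women. The documents supply neither the correlation nor the effect size.

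**Conclusion.** Wrong as written. The sentence gives an independent-samples rank test the task of establishing before-to-after change, and it states no between-arm comparison. If it is followed literally, true size at a nominal 5% falls to about 2%, 0.7% and 0.1% at r = 0.3, 0.5 and 0.7. Near the 80% power point, the power loss is about one seventh, over one third and over two thirds respectively.

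These figures rest on an assumed correlation, assumed 1:1 allocation, two time points and no dropout. The error is in the conservative direction, so a reading that false positives are inflated would be mistaken when the correlation is positive. The defect is confined to the rank-based analysis. It does not discredit repeated measures ANOVA or McNemar as methods for repeated measurements.

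**What to change.** Amend the sentence in the Analysis paragraph of Section B.6.1 as follows:

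- Remove Kruskal–Wallis as a test of before-to-after change.
- For skewed or ordinal outcomes, make the effectiveness analysis a comparison of the two randomized arms on each woman's change score, by the rank-sum test, with the Hodges-Lehmann shift and its 95% CI.
- For any within-arm before-after change in those outcomes, use the Wilcoxon signed-rank test, as Pilot 2 does, and report it as descriptive. Within-arm change does not estimate the randomized effect.
- State which test serves which outcome and which contrast.

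The cost is about one sentence of analysis-plan wording. No new data are needed.
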